For the pilot study, if we do not get the desired number (20) of participants using community recruitment and the UM Institute of Gerontology subject pool (a database of older adults expressing interest in research) within the needed timeframe we will also recruit from the UMClinicalStudies.org website.

For the main study, if we are not meeting desired recruitment numbers, DAAA may send out fliers to participants in their Meals on Wheels (MOW) program asking them to call the Detroit Area Agency on Aging (DAAA) if they are interested in participating in Take Heart. When individuals from the MOW program call DAAA the staff will request permission to send their contact information to Take Heart researchers at the University of Michigan. Contact information from those who agree to this will be relayed to UM via M+Box (which is HIPPAA-compliant), and UM Take Heart researchers will call them with information about the study (following the outgoing phone call path in the recruitment flowchart).

Recruitment from electronic medical records (EMR) at the Detroit Medical Center: The Detroit Medical Center electronic medical record (EMR) systems (Cerner at the Rosa Parks Center and for DMC inpatients; NextGen at University Physicians Group and Cardiology clinic) will be utilized to access potential patients with heart disease and heart disease risk factors (see Inclusion Criteria) using ICD-10 documented clinical diagnoses, and clinician review.

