Data management will be responsible for monitoring interviews completed, which will be done monthly. The interviewers will be sent a list of interviews that have not yet been completed with study participants. This process differs from query letters which request information on specific data items within a form.

Data management will periodically conduct an audit program. A random subset of cases will be selected from the files. In this way, problems with data collection and transmission can be detected early. In addition, data will be monitored for secular trends in data completeness and quality. Study audits will be conducted several times over the course of the study.

Only the study generated ID will used for any and all references to records for purposes of cleaning and overall quality.

***Ame00068213

We added the University of Michigan IRB to the language about the HIPAA waiver for recruitment and language about the HIPAA authorization for enrolled participants recruited from the Detroit Medical Center.

Study Statistical Design

Sample Size Determination:

The primary outcomes of interest in the randomized trial are ED visits and hospitalizations, both overall and heart related. In a sample of 443 patients at a 12 month follow-up, there were significant differences between those that received "take PRIDE" and those that did not in hospitalizations overall (difference of 0.26 times hospitalized) and heart related hospitalizations (difference of 0.41 times hospitalized) and also in overall ED visits (difference of 0.17 visits). The secondary outcome of interest is cardiac symptom experience: number, frequency, and bothersomeness. Several cardiac symptoms will be summed to obtain overall scores: chest pain, shortness of breath, waking with chest pain, waking with shortness of breath, and palpitations. In a sample of 460 patients randomized to the intervention or usual care, researchers found that the change in the number and frequency of symptoms differed significantly between the intervention and comparison group (difference of 0.36 and 1.16 in scores, respectively).

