To detect a 0.15 difference in the change in the number of overall ED visits between the intervention and comparison groups at a 12 month follow-up, a sample size of 188 will be necessary in the intervention and comparison groups for a total sample size of 376 at the end of 12 months. This number will be sufficient to detect a 0.20 difference in hospitalizations and will also be sufficient to detect differences in cardiac symptoms. In a recent iteration of the intervention, the recruitment response rate was 48% and the loss to follow-up was about 20%. Therefore, 1300 subjects will be contacted for participation and 376 subjects will be enrolled.

Analysis of patient outcomes:

Descriptive statistics will be computed for all outcomes overall and stratified by randomized study arms. Health care utilization: Outcome variables including hospitalizations and ED visits will first be assessed as dichotomous variables and will be analyzed using chi-square analyses followed by logistic regression modeling. Because these are count variables, Poisson regression analyses will also be conducted. Cardiac symptoms: The presence of cardiac symptoms will be assessed individually using chi square tests and logistic regression modeling. The cardiac symptoms will also be summed to obtain an overall score of symptoms as well as a score for the frequency and severity. These will be continuous and will be analyzed using analysis of covariance (ANCOVA) and multiple linear-regression modeling assuming normal distributions. If necessary, transformation will be used to ensure normality or Poisson regression will be used if Poisson distributions are found for these variables. They may also be recoded as categorical or ordinal variables and analyzed using chi-square tests and multiple or cumulative logistic regressions.

Functional health status: Functional health status will be assessed using the PROMIS Global Health Scale and/or PROMIS-29. The scores are continuous variables and will be analyzed similarly to the symptoms using ANCOVA and linear regression modeling where the normality assumption is appropriate. They may also be re-coded as categorical or ordinal variables and analyzed using chi-square tests and logistic regressions.

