Intervention dose received: The dose of the intervention will be examined using the logs completed by the health educator. The subject will receive one point for each of 4 sessions attended and a point for each of the three components completed: goal setting, tracking form, and the judgment/reaction. The scores will only be available for the intervention group and will describe average level of participation within the intervention group using frequencies and mean scores.

The components of the intervention: Observation, judgment, goal setting strategies, outcome expectancy and efficacy can also be described individually. Participants in the intervention group may be stratified based on the dose score and outcomes compared using t-tests or chi-square tests of homogeneity to describe impact of dose on outcomes. Instrumental variable approaches to estimating the complier-average causal effect of the intervention will be applied, with compliance defined using two different choices of cut-off on the performance score.

Change over time: The focus of the mixed-model (for continuous outcomes) and GEE (for discrete outcomes) analyses will be to assess changes in dependent measures over time, and whether these changes differ between program participants and "usual care" controls. The effect of time as well as the interaction between time and program participation (program vs. waitlist control) will be included as factors in all models.

Generalizability of the intervention: To determine how effective the intervention would be if duplicated in a similar population, it will be important to examine non-consenters to see if those who choose to participate have certain factors that may be correlated with improved outcomes not present in those who do not participate. Aggregate data from the DMC including demographics, and health care use values will be obtained on those patients that meet the criteria for participation but were not enrolled in the randomized controlled trial to be compared to enrolled participants using t-tests and chi-square tests to discover any differences.

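### The longitudinal models target the between-arm difference in change; with one pre-randomization baseline and one follow-up this loses (1−r)/2 of the information unless baseline means are constrained equal, which the wording leaves open

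*Combined protocol and SAP*

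**What the plan says.** In *Analysis of patient outcomes*, the paragraph on change over time sets the aim of the longitudinal models: "The focus of the mixed-model (for continuous outcomes) and GEE (for discrete outcomes) analyses will be to assess changes in dependent measures over time". The between-arm question it poses is whether the two groups change by different amounts. It then specifies the terms: besides time, "the interaction between time and program participation (program vs. waitlist control) will be included as factors in all models". A program main effect is not listed, and no covariance or working correlation is named.

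*Sample Size Determination* uses the same contrast for ED visits, one of the primary outcomes: "To detect a 0.15 difference in the change in the number of overall ED visits between the intervention and comparison groups" at 12 months, it asks for 188 per arm.

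The Main Study text under *Data Collection* gives two survey times, baseline and 12 months. The Main Study enrollment text places the baseline interview before randomization.

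The longitudinal models are not the only analyses. Hospitalizations and ED visits are first dichotomized (chi-square, then logistic regression) and also analyzed by Poisson regression. No baseline covariate is stated for these, and none of the analyses is named as primary. Symptom scores "will be analyzed using analysis of covariance (ANCOVA) and multiple linear-regression modeling", and the PROMIS scores are handled in a similar way, so these scores get an ANCOVA as well as the longitudinal model.

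**The concern.** Randomization makes the expected baseline difference between arms zero. The observed baseline difference is therefore chance, and the best use of it is to correct the 12-month difference by the part that the within-person correlation predicts. A program + time + interaction model instead subtracts all of it. That is an over-correction whenever the correlation is below 1, and it adds noise to an estimate that is already unbiased.

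What is at stake is precision, not validity: wider intervals and lower power in the mixed and GEE analyses than the same data allow. For symptom and PROMIS scores there is a second consequence. The ANCOVA and the interaction estimate the same effect with different precision, so they can fall on opposite sides of a significance threshold, and the plan does not say which one counts.

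**Working it through.** **Inputs from the documents.** Two time points; baseline before randomization; 188 per arm; target 0.15 for ED visits. **Not in the documents:** alpha, sidedness, power, SD, event rate, and the baseline-to-12-month correlation r. I assume equal variance σ² at both times and show a range for r.

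**The plan's own figure.** The 188 cannot be reproduced without those inputs. It can only be back-solved. With two-sided 5% and 80% power (assumed), the SD of change is 0.15 × √(188/2) / (1.960 + 0.842) = 0.519. Other assumptions give 0.449 (two-sided, 90%), 0.585 (one-sided, 80%) or 0.497 (one-sided, 90%).

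**Variance per patient.**
- Difference in change: 2(1−r)σ²
- 12-month values only: σ²
- Baseline-adjusted or baseline-constrained: (1−r²)σ²

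Change relative to baseline-adjusted: 2(1−r) / [(1−r)(1+r)] = 2/(1+r). Information lost: 1 − (1+r)/2 = (1−r)/2.

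If 188 per arm is right for the change contrast, the adjusted contrast needs 188 × (1+r)/2 per arm for the same power, whatever alpha and power were used. Power at 188 per arm in the last column uses the two-sided 5%, 80% back-solve.

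| r | variance ratio | information lost | n per arm, adjusted (rounded up) | power of adjusted contrast at 188 |
|---|---|---|---|---|
| 0 | 2.00 | 50% | 94 | 98% |
| 0.2 | 1.67 | 40% | 113 | 95% |
| 0.3 | 1.54 | 35% | 123 | 94% |
| 0.5 | 1.33 | 25% | 141 | 90% |
| 0.7 | 1.18 | 15% | 160 | 86% |
| 0.8 | 1.11 | 10% | 170 | 84% |

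**Against ignoring baseline altogether.** The change contrast loses 1 − 1/[2(1−r)]: 38% at r = 0.2, 29% at 0.3, and nothing at 0.5. Above 0.5 it is the better of those two. Against baseline adjustment it loses at every r below 1.

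**Check on counts.** Gamma-frailty Poisson counts were simulated with no treatment effect, 188 per arm and 600 runs per setting, and compared on the log rate-ratio scale. The loss against a baseline-adjusted Poisson model was 47% at r = 0.20 (formula 40%), 32% at 0.33 (33%), 21–25% at 0.50 (25%) and 14% at 0.70 (15%). The formula, derived for means, is a fair guide for counts.

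**The reading without a program main effect.** An exchangeable GEE with time and program × 12-month terms only, so that the arms share one baseline mean, was fitted to the same simulated data. At r = 0.33 its variance was 0.0286, against 0.0288 for the baseline-adjusted model and 0.0422 for the difference in change. Read that way, the plan loses nothing.

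**Why the correlation must be modeled.** Under working independence the constrained model returns the plain 12-month difference, which gives up r² of the information (1 − (1−r²)): 9% at r = 0.3, 25% at 0.5.

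**The case against.** The strongest reply is that the terms as listed are already the efficient model. Time plus time-by-program, with indicator coding and no program main effect, holds the baseline means equal. That reading is open and costs nothing, so the plan cannot be said to have chosen the inefficient estimator. What remains is that the text never says baseline means are constrained. Its stated aim, whether changes differ, points most readers to the conventional three-term model, and the sample size is written on the change scale.

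The second reply is scope. ED visits and hospitalizations also get chi-square, logistic and Poisson analyses. This stands: the loss belongs to the mixed and GEE analyses only. It does not remove the point, because no baseline adjustment is stated for those other analyses either.

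The third reply is that a difference in change is a valid, unbiased estimate and matches the sample size calculation. Also true; the issue is efficiency.

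A reader might go further and argue that the interaction test has 2 df and does not test change at all. That depends on one software coding of the word factors, which can as well mean terms, so the documents do not support it. A reader might also infer that r must be low because recruits were recently hospitalized, from "Cerner at the Rosa Parks Center and for DMC inpatients". That phrase identifies a record system. It does not say that recruits had a recent admission, and recruitment also runs through community flyers and sign-up lists.

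**Conclusion.** The point holds as an efficiency and specification matter. If the longitudinal analyses are fitted as the conventional program + time + interaction model, they lose (1−r)/2 of the available information, about 10% to 50% for r from 0.8 to 0. This assumes equal variances at the two times. It is not a bias, and it does not extend to the trial's other analyses of utilization.

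Three stronger conclusions are tempting and not supported:

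- **A fixed loss of 25–40%.** That is the formula at r = 0.5 and r = 0.2. The documents give no r.
- **A shortfall to about 71% power caused by this choice.** That figure comes from 376 × 0.8 = 301 completers, about 150 per arm, with alpha and power assumed. It reflects enrolling 376 without allowing for the 20% loss, which is a separate matter. At 188 completers per arm, the change contrast has 80% under the same back-solve.
- **A proven mismatch of scales between the targets.** "This number will be sufficient to detect a 0.20 difference in hospitalizations" follows directly on the ED sentence and may be shorthand for a difference in change. The prior figures, introduced by "In a sample of 443 patients at a 12 month follow-up, there were significant differences", are not described closely enough to tell whether they are 12-month values or changes.

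**What to change.** 1. In the change-over-time paragraph, define the effect as the 1-df arm contrast at 12 months with baseline means constrained equal: a 12-month indicator plus program × 12-month indicator, with no arm difference at baseline. State that within-person correlation is modeled in both the mixed model and the GEE, and that working independence is not used. Adjusting a 12-month model for the baseline value is an equivalent choice.
2. In *Sample Size Determination*, describe the ED target as the 12-month difference given baseline, and state the SD, r, alpha and power that go with it.
3. For symptom and PROMIS scores, name this contrast or the ANCOVA as the single effect estimate.

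The cost is SAP wording. The baseline data are already collected, no more patients are needed, and under randomization the expected value of the mean difference is unchanged. The only concession is that the result is described as a 12-month difference rather than a difference in change.
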